STUDY PROPOSAL

Title: SQ53 disinfectant wipes for prevention of catheter related blood stream infection in patients receiving home parenteral nutrition:

A Single Blind Randomized Placebo-controlled Clinical Trial

(NCT04822467)

Principal Investigator: [name]

Co-investigators: [name], [name] [name], [name], RD, [name], [name], RD, [name], [name], [name], [name], [name], [name], [name], RD, [name], NP, [name], PA.

Introduction:

Parenteral nutrition (PN) therapy is an essential component of medical management of patients suffering from intestinal failure. Depending on the underlying etiology and the type of intestinal failure, the duration of parenteral nutrition therapy could range from several weeks to several years, although a substantial proportion of these patients also require lifelong parenteral nutrition support. These patients continue the infusion of PN at their homes and are managed by the Cleveland Clinic's Home PN support team. These patients require Central Venous Catheters (CVC) for prolonged period of time for infusion of parenteral nutrition. The two most commonly used central catheters for TPN infusion are the Peripherally Inserted Central Catheter (PICC) and Tunneled CVCs. Catheter related blood stream infection (CRBSI) is a major complication of long-term CVCs. CRBSI is associated with high morbidity, mortality and healthcare

Protocol version: 1.27.2022

cost. Additionally, CRBSI can also lead to an interruption in nutrient delivery, loss of work and productivity, premature vascular access device removal, and poor quality of life.

Prevention of CRBSI is an important component of clinical management of patients receiving home PN therapy. Several strategies have been adopted to reduce the incidence of CRBSI. A heparin lock solution was used in the past for many years; however, current nutrition society guidelines recommend normal saline locks instead of heparin locks. Published data has suggested that heparin locks have not proven to have a substantial effect on CRBSI prevention, and it paradoxically increases the infection risk due to biofilm production. Antibiotic locks have also been used, although this practice is largely not preferred due to increased risk of infections with resistant microorganisms. Taurolidine is another lock solution which has been studied in the countries outside the United States such as Canada; however, it has not been approved for the use in the U.S. yet.¹

We currently use the ethanol lock therapy which consists of 2ml of 50% ethanol. Multiple single center studies, meta-analysis and the systematic reviews have reported the effectiveness of ethanol lock therapy in prevention of CRBSI. In a retrospective study on the cohort of PN patients from the Cleveland Clinic, we found that Ethanol Lock therapy (ELT) was associated with a decrease in the number of CRBSI-related hospitalizations (10 vs 6 per 1000 catheter days), reduced number of confirmed CRBSI diagnoses with positive culture (3.5 vs 1.6 per 1000 catheter days) and decrease in the number of new catheter requirements.² A study by Zhang et al. reported in their systematic review that ethanol lock was associated with lower CRBSI rates when compared to heparin or normal saline lock.³

By strategically using the ethanol lock therapy daily in our home PN patients, we have been successful in reducing the incidence of the CRBSI in our patient population. However, ethanol lock solution will no longer be available to our patients due to changes in the supply network. The sterile ethanol solution is redirected to a breakthrough use for patients with cardiac hypertrophy which has driven its cost substantially high. Our center had earlier reported a spike in CRBSI in our patients when the ethanol lock solution became unavailable temporarily due to national shortage.⁴ Therefore, it is very important to study and to assess the effectiveness of newer strategies for prevention of CRBSI.

SQ53 is a novel antimicrobial, sporicidal aqueous solution that is based on a platform of quaternary ammonium chloride compounds. Other active components include polymeric biguanide, chlorocresol, bronopol and ethanol. It has been tested against a wide range of bacteria, viruses, spores and fungal pathogens. Extensive laboratory testing has demonstrated the effectiveness of SQ53 impregnated wipes in cleaning surfaces including catheters over a 24 hour plus time period. In addition, it includes no development of VNBC (Viable-but non culturable bacterial colonies) populations or evidence of resistance to the active compounds. SQ53 also received an in vitro evaluation of the irritancy potential using a tissue engineered human skin model and was found to have no potential for skin irritation. In Europe, SQ53 currently has a class 1 CE mark and is cleared and registered under European Union Biocidal Product Regulations in UK, Germany, France, Belgium and Austria. SQ53 is available as a single wipe per pack which is prepared in biocide driven sterilized environment. The pack is easy to open by tearing off the top end and presenting the contents to the operator to remove under sterile conditions.

SQ53 has been studied in India in 148 patients in two groups. Group 1 had the patients who required long term CVC for PN (n = 42, 31 adults and 11 pediatric patients) and dialysis (n=106). Group 2 had the patients who required PN for short duration for postop complications (n=14). The study findings (which are in the publication process) support a substantial improvement in the CRBSI rates **from 131 episodes per 1000 (48 per 365 days) days to 9 episodes per 1000 (3 episodes per 365 days) resulting in an overall 94% reduction**. None of the enrolled patient's experienced local or systemic adverse effect with the use of SQ53 wipes.

[figure not shown]
Study significance:

1. Ethanol Lock Therapy (ELT) which is currently used for prevention of CRBSI is an off-label usage of a commercially available product that will no longer be readily available for patients receiving home parenteral nutrition. Another breakthrough use of ELT has precluded the possibility of ELT use for PN patients. It is critical to identify and explore other agents and alternate therapeutic

approaches to prevent excess morbidity and mortality resulting from preventable CRBSI. SQ53 has shown promising results in CRBSI prevention trial conducted outside the United States.

2. The current study will be a randomized single-blinded placebo-controlled phase III clinical trial for this Investigational new device (SQ53 wipes) intended for the catheter cleaning in patients receiving home parenteral nutrition.
3. With ethanol lock therapy being phased out, there is no currently approved effective and readily available modality available in the United States to prevent CRBSI. On compassionate grounds it is imperative to use and to study SQ53 so that patients can benefit from this clinical trial.

Study design: Prospective randomized single-blinded placebo-controlled clinical trial

*Please note that the randomization will also be stratified by PICC/Tunneled catheter type.

Study objectives:

Primary objective:

1. To determine the effectiveness of SQ53 wipes in prevention of CRBSI in patients receiving home parenteral nutrition.

Secondary objectives:

1. To identify if there are any major or minor adverse effects such as skin irritation associated with the use of SQ53 wipes.

Inclusion criteria and patient recruitment:

1. Adult (age>18) patients requiring home parenteral nutrition support via PICC line or tunneled CVC.
2. Patients will be included via following process:
 - a. All patients managed by CCF HPN team, meeting the inclusion criteria will be sent a letter of information and full informed consent form.
 - i. Letter of information will be a cover letter informing patients about the clinical trial (letter attached)
 - ii. Informed consent form: Standard informed consent form with detailed information about the study as per the Cleveland Clinic guidelines.
 - iii. Letters will be sent in an alphabetical order for 10-15 patients each week to evenly distribute the work burden overtime.
 - b. Patients who are interested to enroll in the study will call our HPN team, and we will answer any questions that these patients might have.
 - i. The consent form will be again sent via email.
 - ii. HPN dietitian will take consent over the phone by using DocuSign and will document it in patient's chart in HPN database
 - iii. HPN dietitian will notify caring NST physician regarding patient's enrollment in the trial.

- c. HPN dietitian (or NST physician or both) will classify patient in either a High Risk, Low Risk or New Patient Category via specific criteria.
 - i. **Identification of high-risk patients** which will be determined by the following criteria:
 - 1. History of one or more CRBSI infection in the past 6 months
 - 2. Immunocompromised state increasing the infection risk
 - a. Clinical determination based on comorbidities such as HIV, immunosuppressant medications, and steroids (prednisone >40mg per day)
 - 3. History of multiple catheter exchange in the past (greater or equal to 2 within the past 6 months) with difficult access
 - a. This determination to be made based on patient's history
 - ii. Identification of Low risk patients:
 - 1. Patients who do not meet High-risk criteria will be classified as Low risk patients
 - iii. New patients:
 - 1. New patients are the patients who are newly started on PN during their in-patient stay and those who have been on PN less than 6 months unless they had CRBSI in the time frame.
 - 2. These patients will receive information about the clinical trial by RNs who provide education as standard of care.
- d. Patients can also be enrolled in the study at the time of outpatient visit, or before discharge from the hospital.
- 3. Cleveland Clinic Home Infusion Pharmacy (CCHIP) will be informed about patient's enrollment and the risk category (High vs Low vs New patient) and the catheter type (PICC or tunneled)
 - a. CCHIP will perform stratified randomization and assign the patient to either Treatment (SQ53) or PLACEBO (Alcohol wipes) group.
- 4. Treatment group will also have the SQ53 impregnated wipe used on a remote site to check for hypersensitivity and any other skin reactions before it is deemed safe to use routinely in that patient.

5. All enrolled patient will need to agree to reach out to Home Nutrition Pager which is available 24x7 in case of noted adverse effect – this is standard of care for home PN patients.

Exclusion criteria:

1. Age less than 18 years
2. Women known to be pregnant (patient will be asked verbally- no pregnancy test will be performed)
3. Women of childbearing age who are planning a pregnancy
4. Women who are breastfeeding
5. Patient's refusal to enroll in the study at any point in time
6. Patients who refuse to use disinfectant wipes daily.
7. Patients who use port for their PN infusion.
8. Patients who are enrolled in other clinical trials with investigational drugs or device

Blinding and Randomization:

- **Blinding:** This will be a single blinded study and the NST-providers will be blinded to the treatment arm that the patient is assigned to. A clinician will initially interview the patient and at the time of enrollment into the clinical trial, obtain an informed consent after which the patient will be enrolled in the study.
- **Blinding the patients is not possible** due to several reasons:
 - o SQ53 and alcohol wipes will have labels on them
 - o differences in physical characteristics (smell) which are distinct for alcohol wipes and SQ53
 - o therefore, it is unfeasible to blind patients to the intervention.
- **However,** despite being an unblinded study, outcome of our study is not likely to be affected as the primary outcome measure is diagnosis of CRBSI which is based on the Positive Blood Culture and is not very likely to be impacted by a placebo effect.
- **Randomization with a placebo:** Once patients are enrolled into our study, patient's information will be discussed with the pharmacy who will assign the patient to either a treatment or a placebo group.

- Patients will be randomized in 1:1 ratio to receive either SQ53 or placebo. The randomization process will be stratified randomization, followed by blocked randomization in each stratum. Stratification will be done on two factors: CRBSI risk category and catheter type. CRBSI risk categories will be determined by the clinicians or NST staffs 1. High risk (1 or more CRBSI in previous 6 months) 2. Low risk (no CRBSI in previous 6 months) 3. New patient. Catheter types will be 1. Tunneled central catheters 2. Non-tunneled central catheters. The design has $3 \times 2 = 6$ strata. Blocked randomization will subsequently done in order to avoid serious imbalance in the number of participants assigned to treatment or placebo group. The block sizes will be determined by Cleveland Clinic Home Infusion Pharmacy.

Intervention:

Patients who qualify to enroll in the trial and sign an informed consent will be enrolled and will be eligible to receive either the intervention or the placebo. Providers will be blinded to which group patient is assigned to.

- Pharmacy (Cleveland Clinic Home Infusion Pharmacy will perform randomization and will assign patients to the groups)
- **All patients in the study will receive the wipes (Treatment group = SQ53 wipes, Placebo = alcohol wipes)**
 - o Provide packs of sterile wipes to the patient for daily use (**external use only**)
 - o Wipes should be used daily, as well as, when the dressing is changed, by wiping the catheter surface and hubs for at least 15 seconds
 - o **Daily use:** Patients will be given instruction to clean the exterior and the caps of the intravenous catheters by following a sterile technique. This should be done before and after each use (i.e. PN infusion)
 - o **At the time of dressing change:** Standard practice is to change the dressing every week. At this time the patient will use wipes to clean the catheter exit site and skin around the catheter exit site, catheter exterior and catheter caps prior to applying the new dressing
 - o Wipes will be provided to the patient free of cost (material will be sponsored by the JVS company)

- Patients in both the groups will continue to use the standard care: i.e. ethanol (curos) caps, saline locks.

Data collection:

1. A registry of enrolled patients will be prepared. CCF HPN service has an approved database of patients receiving home parenteral nutrition. There are no additional HPI that will be collected as a part of enrollment in the study. The patient data is already collected into a password protected HPN database as current standard of practice. This data is routinely collected and updated by HPN dietitians.

Sample data sheet of primary objectives (data in *italics blue font* is for example):

Patient Nomenclature:				
SQ53/Treatment Group: Patient T1, Patient T2....				
Placebo Group: Patient C1, Patient C2....				
	Pre vs Post SQ53 trial enrollment	Number of Confirmed CRBSI in 6 months	Number of total admissions for CRBSI in 6 months	Number of catheters changed due to CRBSI in 6 months
Patient T1	Pre	2	3	0
	Post	0	1	0
Patient T2	Pre			
	Post			
Patient C1	Pre	0	1	0
	Post	1	1	1

Patient C2	Pre			
	Post			
Patient C3	Pre			
	Post			

Data protection, processing and, analysis of the data:

1. CCF HPN service has an approved database of patients receiving home parenteral nutrition. The patient data is already collected into a password protected HPN database as current standard of practice. We will use REDCap for data entry for analysis. All data will be password protected.
2. We plan to perform both "**Per Protocol**" and "**Intention to treat analysis**".
3. Patients whose compliance is less than 90 percent will be excluded from Per Protocol analysis; however, those patients will be accounted in intention to treat analysis. Patients who developed skin reaction in remote site (e.g., forearm) will be excluded from Per Protocol analysis, but will be included in intention to treat analysis
 - a. Compliance will be determined by HPN dietitian at the time of phone/virtual visit encounters: patient will be asked about their disinfectant wipe use and compliance.
4. Our primary outcome measure (as listed in above data sheet) will be differences in the CRBSI rate at 6 months after patient enrollments into the trial (i.e. SQ53 use). We will also perform sub-analysis by utilizing patients as their own controls. Please see the detailed timeline below.
5. We will also analyze the differences in the number of admissions for CRBSI (which would include admission with suspect CRBSI), as well as, overall number of catheters changed for confirmed and suspected CRBSI.
6. We will perform Poisson Regression analysis to compare the rates and 95 % confidence interval of the differences in CRBSI rates and CRBSI admissions.
7. We will also perform a descriptive analysis identifying the most common microorganisms causing the CRBSI in the periods both before and during the SQ53 therapy.
8. We will also perform a survival analysis to plot a Kaplan-Meier curve

9. We will collect mortality data of patients. We will report an overall mortality, as well as, CRBSI-specific mortality in patients using SQ53 for CRBSI prevention.

Sample size and power calculation:

1. In the un-published study conducted in India SQ53 has been reported to reduce the CRBSI rate by 94%. We expect this effect size to be lower in our cohort. We performed our sample size calculation by utilizing the data reported in our previous study which reported CRBSI rates in high risk PN patients (Pre-ELT CRBSI rate= 3.53 and post-ELT 1.65 per 1,000 catheter days). Considering current CRBSI rate in our high-risk population to be 1.65 per 1000 catheter days, we will need a sample size of 46 patients to identify a 50% reduction in CRBSI rate with alpha of 0.05 and 80 % power.
2. To account for the patient attrition due to mortality, lost follow up and non-compliance (for per-protocol analysis), we would like to increase our sample size by 30% to this estimated calculation and would need to enroll 30 patients in each group of our study to make determinations of differences with statistical significance.

Safety concerns: Risk to the study participants: Minimal

1. Our study is a single blinded randomized placebo-controlled phase III clinical trial which utilizes disinfectant wipes which are meant for external use only. These wipes have proven to be safe in the in-vivo and in-vitro studies.
2. No major adverse effect has been reported in previous clinical trial.
3. Current data suggest that SQ53 has no potential for skin irritation; however, if a patient experiences hypersensitivity skin reaction to any of the ingredients in the formula, then those patients will be excluded from the study and use of wipes will be discontinued.
4. Collected PHI data will be securely protected on the Cleveland Clinic Network drive.

Timeline:

Please see below a simplified timeline for this project.

Time Period	Activity
-------------	----------

	
Project Lead: [name]
 
Project mentors: [name] and [name]
 
Project team members: [name], [name], [name] and [name], [name], [name]

June 2020 - Sept 2020	
 1. Protocol and team development 2. Investigational New Drug (IND exemption process) 3. FDA exemption given by CCF IDE office considering the wipes as low risk device 
Personnel responsibility:
 
Above steps have been completed

Oct 2020 – Nov 2020	
 1. Protocol submission to CHN & budget acquisition 2. Protocol submission to DDSI 3. Protocol submission to IRB 
Personnel responsibility:
 
Above steps have been completed.
 
 - Protocol for IRB/CHN/DSFI submission is ready - Cover letter is ready - Informed consent document is ready - Budget is done
Nov 2020 – Dec 2020	
 1. Once IRB is approved: send letters to patients 2. Obtain informed consent and enroll patients 3. Risk category assessment 4. Baseline data collection 5. Randomization 6. Shipment of SQ53 or Placebo supply 
Personnel responsibility:
 
 1. Sending letters to patients: 
 - Letter has been drafted and ready, to be printed and mailed to the patients by study coordinator

	
2. Obtain informed consent
 
 - HPN dietitian 
3. Risk category assessment
 
 - HPN dietitian & NST staff 
4. Baseline data collection
 
 - HPN team, Nutrition Fellows, Study coordinator 
5. Randomization
 
 - DDSI statistician / CC Home infusion Pharmacy 
6. Supplying SQ53 and placebo wipes
 
 - CC Home infusion pharmacy
Dec 2020 to June 2021	
1. Continuation and monitoring phase of the study
 
2. Answer patient's concerns and collect data regarding specific side effects (if any)
 
3. Continue standard routine follow up: i.e. with labs, or during phone encounters
 
Personnel responsibility:
 
 - HPN dietitian, NST staff and Nutrition fellows
June 2021	
1. Perform interim analysis of the data
 
Personnel responsibility:
 
 - DDSI statistician
July 2021 to Dec 2021	
1. Continue the study for another 6 months and continue to enroll the patients
 
Personnel responsibility:
 
 - HPN dietitian, NST staff and Nutrition fellows
Jan 2022	
1. Final Analysis of the data
 
2. Reporting of the study findings
 
Personnel responsibility:
 
 - Statistical analysis: DDSI statistician

	- Reporting: All investigators
--	--------------------------------

References:

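### A skin check done after allocation in the SQ53 arm only marks the arm, adds skin data in one arm and makes a per-protocol exclusion one-sided

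*Combined protocol and SAP*

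**What the plan says.** Under Inclusion criteria and patient recruitment, item 3a gives allocation to the home infusion pharmacy: "CCHIP will perform stratified randomization and assign the patient to either Treatment (SQ53) or PLACEBO (Alcohol wipes) group". Item 4 follows: "Treatment group will also have the SQ53 impregnated wipe used on a remote site to check for hypersensitivity and any other skin reactions". The stated purpose is to establish that the wipe is safe for that patient before routine use. No section describes a corresponding check with the alcohol wipe.

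Four other parts of the protocol bear on this:

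- **Blinding.** Blinding and Randomization states that "the NST-providers will be blinded to the treatment arm that the patient is assigned to", and Intervention repeats it: "Providers will be blinded to which group patient is assigned to". Patients are not blinded, because the wipes are labelled and smell different: "therefore, it is unfeasible to blind patients to the intervention".
- **Secondary objective.** Study objectives lists one: "To identify if there are any major or minor adverse effects such as skin irritation associated with the use of SQ53 wipes".
- **Collection of side effects.** The Timeline entry for the monitoring phase gives this work to dietitians, nutrition fellows and NST staff. Item 5 of the recruitment section has every enrolled patient agree to call the nutrition pager if an adverse effect is noted.
- **Handling of reactors.** The data analysis section, item 3, drops patients with a remote-site reaction from the per-protocol set and keeps them in the intention-to-treat analysis. Safety concerns, item 3, says that patients with a hypersensitivity skin reaction leave the study and stop the wipes.

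**The concern.** The provider blind is the only blind in this trial. A procedure ordered for every patient in one arm and none in the other discloses the arm whenever a blinded provider learns of it.

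Blinding and Randomization argues that a culture-based outcome is unlikely to respond to a placebo effect. That argument concerns patients. It does not cover a provider's decision on when to draw a culture. Nor does it cover the further outcomes in item 5 of the data analysis section, which count admissions for suspected CRBSI and catheters changed for suspected CRBSI. Both depend on provider judgement.

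Two other consequences follow from the same asymmetry. Skin irritation is the example named in the secondary objective, and one arm receives an exposure and an inspection that the other does not. In addition, a reason for leaving the per-protocol set exists in one arm only, so the two per-protocol groups are not selected in the same way.

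**Working it through.** The plan gives no figure on this point, so there is none to reproduce. The check is a reading of the sections together, followed by an illustration on assumed values.

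**Timing.** Allocation is item 3a. The check is item 4 and is defined by assigned group. It therefore follows randomization and depends on its result.

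**What the check reveals.** Allocation is 1:1 with 30 patients planned per arm (Sample size and power calculation, item 2). The check is ordered for 30 of 30 SQ53 patients and 0 of 30 controls, so a patient known to have had it is on SQ53 with certainty.

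**Who learns of it.** The protocol does not say who applies or reads the check, where it is recorded, or how it is kept from NST providers. NST staff are among those who collect side effects. Disclosure is therefore a plausible inference, not a stated fact.

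**Illustration.** The documents give no reaction probability, so p is assumed at 2% to 20% per check.

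- Chance of at least one remote-site reaction among 30 SQ53 patients: 1 − (1 − p)^30. In the control arm it is 0 by construction.
- Expected SQ53 per-protocol set before non-compliance: 30 × (1 − p), against 30 for control.
- Patients detected as reactors if both wipes had the same p, checks were independent, and each arm had one routine check with SQ53 having one more: 1 − (1 − p)² against p, a ratio of 2 − p.

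| Assumed p | At least one remote-site reaction, SQ53 | Expected per-protocol set, SQ53 v control | Detected, SQ53 v control | Ratio |
|---|---|---|---|---|
| 2% | 45% | 29.4 v 30 | 4.0% v 2% | 1.98 |
| 5% | 79% | 28.5 v 30 | 9.8% v 5% | 1.95 |
| 10% | 96% | 27.0 v 30 | 19% v 10% | 1.90 |
| 20% | 99.9% | 24.0 v 30 | 36% v 20% | 1.80 |

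The ratio column is close to a worst case, because it allows only one routine check. Under Intervention, wipes are applied to exit-site skin at dressing changes, normally weekly. Over 6 months that is about 182.5 / 7 = 26 skin exposures. If each counted equally, one more would give 27 / 26 = 1.04, or about 4% more exposures.

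**Direction.** The extra check raises the SQ53 count. If reactors then stop using the wipe, later SQ53 reactions fall. The net sign is not determined. If p is 0, as the earlier study summarised in the Introduction reports, the count effect and the one-sided exclusion vanish, but the check still marks the arm.

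**The case against.** The strongest reply is that the check does little harm beyond what is already there. Patients know their wipe, are asked about its use by dietitians, and have round-the-clock contact with the team. The sample data sheet codes patients T or C. A provider has several ways to learn the arm without this check, and the primary outcome requires a positive culture. All of that stands, and it keeps the point small. It does not remove the point: those routes are incidental, whereas this one is written into the protocol for every SQ53 patient.

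A reader might infer that the check does unblind NST providers. The documents do not support that. The pharmacy holds the allocation and supplies the wipes, and the check could be done without an NST provider knowing.

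A reader might also infer that a planned comparison of skin reactions is biased. None is specified. The secondary objective is descriptive and concerns SQ53, and the data analysis section compares CRBSI rates, CRBSI admissions and catheter changes. For finding SQ53 reactions, an extra SQ53 check helps. What remains is that an informal comparison of skin findings by arm would mix two sources, one of which exists in one arm only.

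The asymmetry also has a reason, since a new product is being screened before routine use. That justifies the check in SQ53 patients. It does not justify having none in controls, and a mirrored check leaves the screening intact.

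**Conclusion.** The point holds as a cheap improvement, not as a threat to the primary result. Three things follow directly from the text: the check is done after allocation and in the SQ53 arm only, it adds skin ascertainment in that arm only, and it makes the per-protocol exclusion for remote-site reactions one-sided. Disclosure of the arm to blinded providers is an inference. It rests on the absence of any described safeguard and on NST staff helping to collect side effects.

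The procedural imbalance is 30 of 30 against 0 of 30. The resulting bias cannot be sized. The inflation of detected skin reactions could lie anywhere from about 4% to nearly twofold under the assumptions shown, or be reversed by screening. Any effect on confirmed CRBSI would act through provider decisions and is indirect. Whether the one-sided exclusion shifts the per-protocol CRBSI comparison depends on whether reactors differ in infection risk, on which the documents are silent.

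**What to change.** - Do the same remote-site check in both arms after allocation, each patient using the assigned wipe, and record it on one form that does not name the wipe.
- State who performs, reads and records the check, and how the result is kept from NST providers.
- Tabulate remote-site reactions separately from reactions during routine use, by arm.
- Apply the per-protocol exclusion for remote-site reactions identically in both arms.
- Reconcile item 3 of the data analysis section, which keeps reactors in the intention-to-treat analysis, with item 3 of Safety concerns, which has them leave the study.

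The cost is one alcohol wipe and one question per control patient, plus a few lines of text. No extra staff are needed for the mirrored check, and the SQ53 safety check is unchanged. The limit should be stated: having the check would no longer identify the arm, but anyone who sees or smells the wipe would still know it. Fuller protection would need a reader outside the NST, which is a separate decision with its own staffing cost.

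### The background catheter lock is described in two ways with no switch date, so the within-arm Pre/Post CRBSI comparison can mix the loss of ethanol lock with the wipe effect

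*Combined protocol and SAP*

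**What the plan says.** On the lock in use, the combined protocol and SAP says:

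- Introduction: "We currently use the ethanol lock therapy which consists of 2ml of 50% ethanol". The same section gives the frequency: "By strategically using the ethanol lock therapy daily in our home PN patients". It then says that "ethanol lock solution will no longer be available to our patients due to changes in the supply network".
- Study significance, item 1: "Ethanol Lock Therapy (ELT) which is currently used for prevention of CRBSI is an off-label usage of a commercially available product". Item 3 opens: "With ethanol lock therapy being phased out".
- Intervention, last bullet: "Patients in both the groups will continue to use the standard care: i.e. ethanol (curos) caps, saline locks".
- Sample size and power calculation, item 1: the post-ELT rate of 1.65 per 1,000 catheter days is taken as the present rate in high-risk patients. This fits ethanol lock still being in use when the plan was written.

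On the analyses that compare periods:

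- Data collection: the sample data sheet has a Pre and a Post row, each covering 6 months, for SQ53 and placebo patients alike. Its columns are confirmed CRBSI, CRBSI admissions and catheter changes. None records the lock.
- Data protection, processing and analysis, item 4: after the primary between-group comparison at 6 months, "We will also perform sub-analysis by utilizing patients as their own controls". Item 7 describes the organisms before and during SQ53 use.
- Blinding and Randomization: the strata are CRBSI risk category and catheter type. Lock type is not a stratification factor, and no covariate is named for the Poisson model in item 6.

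**The concern.** A patient on daily ethanol lock cannot continue saline locks. Either the Introduction no longer describes patients at enrolment, or the Intervention bullet describes a new lock as an ongoing one. In the second case the Pre window is wholly or partly ethanol-lock time and the Post window is saline-lock time.

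The plan itself treats ethanol lock as strongly protective. It quotes a rate that fell by about half with the lock, and it reports a rise in infections during a temporary shortage. If the lock is lost between the windows, the Post rate would be expected to rise in both arms whatever the wipe does. A Pre/Post change within the SQ53 arm would then combine two effects acting in opposite directions. An effective wipe could look weak or useless, and the data sheet as drawn would not let a reader see why. The before/during organism description has the same weakness.

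**Working it through.** **Can the two descriptions be read together?** There are two readings.

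1. Sequential: ethanol lock before enrolment, saline after, because of the phase-out. The texts then fit apart from the verb in the Intervention bullet, and the windows are on different locks.
2. Patients were already on saline at enrolment. The bullet is then right and the Introduction is out of date for them. The Pre window is on saline only if the switch came at least 6 months earlier.

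No switch date is given, so the text does not settle which applies. Letters go out in weekly batches of 10–15, and the Timeline continues enrolment into July–December 2021. The share of Pre time on ethanol lock may therefore differ between patients.

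**Inputs.** The plan gives no figure for the own-control analysis, so there is none to reproduce.

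- Rates per 1,000 catheter days in high-risk patients (sample size section): 3.53 before ELT, 1.65 after. Ratio 3.53/1.65 = 2.14; reduction 1 − 1.65/3.53 = 53%. The Introduction's rounded 3.5 and 1.6 give 2.19.
- Planned SQ53 effect: 50% reduction, rate ratio 0.50.
- Assumption: 3.53 applies to saline-lock time. The documents do not say which lock, if any, lay behind it.
- Assumption: all Post time is on saline, as the Intervention bullet states.

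**Apparent Post/Pre ratio.** Let s be the share of Pre time on ethanol lock.

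Pre rate = 1.65s + 3.53(1 − s)

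SQ53 ratio = (0.5 × 3.53)/Pre rate; placebo ratio = 3.53/Pre rate

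| s | Pre rate | SQ53 Post/Pre | Placebo Post/Pre | SQ53 ÷ placebo |
|---|---|---|---|---|
| 0 | 3.53 | 0.50 | 1.00 | 0.50 |
| 0.25 | 3.06 | 0.58 | 1.15 | 0.50 |
| 0.50 | 2.59 | 0.68 | 1.36 | 0.50 |
| 0.75 | 2.12 | 0.83 | 1.67 | 0.50 |
| 1 | 1.65 | 1.07 | 2.14 | 0.50 |

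With s = 1, the SQ53 arm goes from 1.65 to 0.5 × 3.53 = 1.765, an apparent rise of 7%. The last column returns the true effect whatever s is, because neither arm uses the trial wipes in the Pre window and randomisation makes the Pre rates equal in expectation.

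**Sensitivity to the assumed saline rate, s = 1.** A rate of 2.0 gives 0.5 × 2.0/1.65 = 0.61; 2.5 gives 0.5 × 2.5/1.65 = 0.76.

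**What it takes to hide the whole effect (ratio of at least 1).** At 3.53: 1.765 ≥ 3.53 − 1.88s, so s ≥ 1.765/1.88 = 0.94. At s = 1: the saline rate must be at least 2 × 1.65 = 3.30.

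**Expected events.** For 30 patients per arm and 182.5 days, 5,475 catheter days per window, with s = 1 and a saline rate of 3.53: SQ53 9.0 Pre and 9.7 Post; placebo 9.0 Pre and 19.3 Post. With no lock change and a Pre rate of 1.65, SQ53 Post would be 4.5. These counts assume a full Pre window for everyone and high-risk rates throughout.

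**Precision of the arm-by-period contrast.** With independent Poisson counts, the standard error of the log ratio of ratios is √(1/9.03 + 1/9.66 + 1/9.03 + 1/19.33) = 0.61. The Post-only comparison between arms gives √(1/9.66 + 1/19.33) = 0.39.

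**The case against.** The strongest reply is that this does not touch the primary result. The primary outcome is the between-group difference in a 1:1 randomised trial in which both arms are to have the same background care. That stands in full. A reader might infer from the lock conflict that the trial's main conclusion is biased; the documents do not support that. Nor do they support adding lock type to the primary model, because the Intervention section puts both groups on saline locks.

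A reader might also infer that the Pre/Post comparison would hide the whole planned effect. That holds only in a corner: about 94% or more of Pre time on ethanol lock and a saline-lock rate near 3.53. The Introduction says heparin locks were used for many years and raised infection risk, so 3.53 need not be a saline rate. It also comes from high-risk patients, whereas the trial takes low-risk and new patients too. This part of the reply stands, and the 1.07 is an upper-end illustration.

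Third, the planned data already contain a control, because placebo patients have Pre and Post rows. That is correct and shapes the fix. However, item 4 does not say that the own-control analysis will be read against the placebo arm.

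Fourth, the phase-out may make the two descriptions sequential. It may, but the windows then differ, which is the concern itself.

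Finally, the data sheet is only a sample, and the HPN database may already hold the lock. Its fields are not listed, so this can be neither confirmed nor excluded.

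**Conclusion.** The point holds for the secondary period comparisons only. The plan gives two descriptions of the background lock and no switch date, and it has no stated provision for a lock change between the windows. The within-arm own-control sub-analysis and the before/during organism description can therefore mix the loss of ethanol lock with the wipe effect. The randomised 6-month comparison is not biased.

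The size is illustrative. With a true 50% reduction and 3.53 assumed for saline-lock time, the apparent SQ53 Post/Pre ratio lies between 0.50 and 1.07, depending on an unstated share of Pre time on ethanol lock. With all Pre time on ethanol lock but lower assumed saline rates of 2.0 and 2.5, it is 0.61 and 0.76. Partial masking is the more defensible reading; complete masking needs both extremes together. The plan should be changed, because a misleading Pre/Post result is possible as it is written and the remedy is cheap.

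**What to change.** 1. Reconcile the Introduction and Study significance with the last bullet of the Intervention section on the lock in use before and after enrolment, and give the date or period of any switch. Which lock patients receive is for the investigators.
2. Record lock type for the Pre and Post windows and the date of any switch.
3. In item 4, define the Pre/Post analysis as an arm-by-period contrast: the ratio of the Post/Pre rate ratios, SQ53 against placebo, from the rows already planned for both arms. Allow for repeated counts within patients.
4. Where same-lock catheter days exist in both windows, use them in a sensitivity analysis. This cannot be the main analysis: under a full switch there are no such Pre days, and a lock term would be collinear with period.
5. State that a Pre/Post change within the SQ53 arm across a lock switch will not be reported as an SQ53 effect.
6. In item 7, describe organisms before and during by arm, with the lock noted.

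The cost is one data field, if the HPN database does not already hold it, and some analysis wording. The contrast is less precise than the between-arm Post comparison (standard error 0.61 against 0.39 on the log scale in the illustration), so it remains supportive. Patients who start PN in hospital have no home Pre window, and others on PN for under 6 months have only a partial one, so they contribute little. Enrolment and the primary comparison do not change.
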